## 4. LIST OF ABBREVIATIONS

AE	Adverse Event
BMS	Bristol-Myers Squibb
CBC	Complete Blood Count
CMP	Comprehensive Metabolic Panel
CTCAE	Common Terminology Criteria for Adverse Events
DLT	Dose Limiting Toxicity
DSMB	Data and Safety Monitoring Board
GBM	Glioblastoma
IV (or iv)	Intravenously
ICS	Investigational Chemotherapy Service
IO	Immunotherapy
IRAE	Immune Related Adverse Event
MTD	Maximum Tolerated Dose
NCI	National Cancer Institute
NSCLC	Non-Small Cell Lung Cancer
OS	Overall Survival
PBMCs	Peripheral Blood Mononuclear Cells
PD	Progressive Disease
PFS	Progression Free Survival
PRTBTC	Preston Robert Tisch Brain Tumor Center
RCC	Renal Cell Carcinoma
SAE	Serious Adverse Event
SD	Stable Disease
SRS	Stereotactic Radio Surgery
TNBC	Triple Negative Breast Cancer

## 5. PROTOCOL SYNOPSIS AND RESEARCH SUMMARY

### 5.1. Purpose

A phase II study of neoadjuvant nivolumab and ipilimumab in patients with surgically-resectable, solid tumor brain metastases is planned to address the following objectives.

Primary Objectives:

1. Assess the feasibility of neoadjuvant ipilimumab and nivolumab treatment before surgery and SRS in patients with solid tumor brain metastases as measured by the proportion of patients who have their surgery delayed or surgery never occurs.
2. Demonstrate that neoadjuvant immunotherapy will increase proliferation of circulating T-cells compared to baseline measurements.

Exploratory Objectives:

1. Describe the survival of patients with solid tumor brain metastases receiving neoadjuvant ipilimumab and nivolumab followed by surgery and SRS.
2. Describe the time to local intracranial progression.
3. Describe the time to distant intracranial progression.
4. Describe the time to overall intracranial progression.
5. Describe progression-free survival.
6. Quantify the rate of radiation necrosis.
7. Describe the immune expression profile of patients treated with neoadjuvant ipilimumab and nivolumab.

Hypotheses

This is a hypothesis testing protocol designed to test the following hypotheses:

1. Neoadjuvant immunotherapy will not delay surgical resection for patients with solid tumor brain metastases.
2. Neoadjuvant immunotherapy will increase Ki67 on circulating PDL-1+/CD8+ T-cells among patients with solid tumor brain metastases.

### 5.2. Background and Significance

As treatments for primary tumors improve and patients survive longer, the potential for primary tumors to metastasize increases, creating a need for newer and better therapeutic strategies for patients with metastases. Currently, up to 30% of cancer patients will develop at least one brain metastasis [1]. Current standard of care therapies include resection and stereotactic radiosurgery (SRS) followed by a variety of maintenance treatments. Progression free survival (PFS) and overall survival (OS) rates for patients with brain metastases are modest at best. For example, lung

cancer, breast cancer and melanoma patients with untreated metastases have median survival rates of 12 months [2], 13.8 months [3, 4], and 9.8 months [5], respectively, motivating a need for novel therapeutic approaches within these patient populations. Recent approaches for treating brain oligometastases (few, small metastases) include immunotherapies, but the timing as to when to initiate immunotherapy is still up for debate. Most studies have focused on adjuvant immunotherapies, following surgical resection and SRS; however, giving immunotherapies after surgery may reduce T-cell receptor modulation, activating fewer tumor-specific T cells leading to a less robust immune response. Providing immunotherapies in the neoadjuvant setting, where antigenic burden is higher in the brain, could result in enhanced T-cell receptor modulation, and therefore more robust activation of tumor-specific T cells and an overall more effective immune response. Indeed, a limited number of studies have shown improved outcomes for patients receiving immunotherapy in the neoadjuvant setting, demonstrating neoadjuvant immunotherapy merits further investigation.

The two most common immunotherapy checkpoint blockades are PD-1/PD-L1 and CTLA-4. Bristol Meyers Squibb (BMS) has developed compounds targeted at blocking each of these checkpoints: nivolumab (PD-1) and ipilimumab (CTLA-4). This is a feasibility and efficacy study testing the combination of neoadjuvant nivolumab and ipilimumab in patients with solid tumor brain oligometastases as described in Section 5.3.

### **5.3. Design and Procedure**

After providing informed consent, up to 20 eligible participants with surgically-resectable, solid tumor brain metastases will be treated. Participants will receive a single dose of neoadjuvant nivolumab and ipilimumab 7 days ( $\pm$  3 days) prior to surgical resection. Nivolumab will be given at the FDA-approved dose of 3 mg/kg; ipilimumab will be given at the FDA-approved dose of 1 mg/kg. Patients will then continue to have standard of care SRS 3 weeks ( $\pm$ 3 weeks) after surgery. See Section 6 for the study schema.

### **5.4. Selection of Subjects**

Please see Section 11 for a list of all inclusion and exclusion criteria.

### **5.5. Duration of Study**

Patients will be on study for up to 18 months after initiation of study treatment.

[figure not shown]
### **5.6. Data Analysis and Statistical Considerations**

Feasibility will be assessed by the proportion of patients who have their surgery delayed. With the checkpoint inhibitors being administered on Day -7, the surgery is scheduled for Week 1, Day 1 ( $\pm$  3 days). *Surgery will be considered delayed if it never occurs or occurs after Day 4 (i.e. Day 1 + 3).* The proportion of patients experiencing surgical delay as defined in Section 15.5.1.1 will be computed as the number of patients with delay divided by the total number of patients per arm. Methods developed for continuous monitoring of toxicity will assess whether the number of surgical delays is excessive. Monitoring rules based upon Pocock monitoring rules are provided in Section 15.5.1.2.

A one-sample t-test will assess whether significant changes fold-change in Ki67 levels between baseline and Day 1 occurred.

Kaplan-Meier methodology will be used to graphically display survival and progression-free survival; whereas, cumulative incidence curves will be used to graphically display time to local intracranial progression, time to distant intracranial progression, and time to overall intracranial progression as defined in Section [15.6.2](#).

## 6. STUDY SCHEMA

Arm	Study Drug	Study Drug Administration Schedule	Dose
1	Nivolumab	7 days (±3 days) prior to surgery	3 mg/kg
1	Ipilimumab	7 days (±3 days) prior to surgery	1 mg/kg

## 7. BACKGROUND AND SIGNIFICANCE

### 7.1. Study Disease

Brain metastases are 10 times more common than primary brain tumors and arise in 10-35% of adult cancer patients [6], affecting approximately 200,000 adult cancer patients each year in the US [7]. Though brain metastases can develop from any primary tumor, the most frequent primary tumors to metastasize to the brain originate in the lung, skin (melanoma), kidney, and breast [7]. Given the heterogeneity of brain metastases, prognosis varies widely (anywhere from a few months to over a year), and is largely dependent on neurological performance status at the time of diagnosis, and the primary tumor location [6]. In a recursive partitioning analysis of prognostic factors in patients with brain metastases, the best median survival was 7.1 months, while the worst median survival was 2.3 months [8]. According to a multicenter, retrospective analysis of 3940 patients with brain metastases, median overall survival varied with primary tumor location, with a median OS of 7 months for NSCLC, 6.74 months for melanoma, 9.63 months for RCC, and 13.8 months for breast cancer [9]. Despite evolution of the standard of care for patients with brain oligometastases from whole brain irradiation and systemic therapy to include some combination of surgical resection, SRS, and carefully selected systemic therapy [7], prognosis remains poor for these patients with a median survival of around 10.8 months [10]. Clearly, there is a need to identify new therapies for patients with brain oligometastases.

### 7.2. Study Agent

Immunotherapies, including checkpoint inhibitors, have shown promise for treating a variety of tumors, including CNS tumors [11]. The PD-1/PD-L1 and CTLA-4 checkpoint blockades are often responsible for preventing an effective anti-tumor immune response by inducing T-cell senescence. Checkpoint inhibitors, such as pembrolizumab (Keytruda®) and nivolumab (Opdivo®), inhibit PD-1 on T-cells to delay T-cell senescence by disrupting PD-1/PD-L1 interaction. Other checkpoint inhibitors, like ipilimumab (Yervoy®), bind to CTLA-4 on T-cells to prevent T-cell inactivation, promoting a more robust immune response. Both nivolumab and ipilimumab currently have FDA approval for various indications outlined in Sections 7.2.1 and 7.2.2. Nivolumab and ipilimumab will be administered a single time at the FDA approved doses of 3 mg/kg and 1 mg/kg, respectively.

#### 7.2.1. Nivolumab

[figure not shown]
Nivolumab (Opdivo®) is a human monoclonal antibody that blocks the interaction between PD-1 and its ligands, programmed death-ligand 1 (PD-L1) and programmed death-ligand 2 (PD-L2). Nivolumab is currently FDA approved for unresectable, metastatic, and progressive melanoma and progressive metastatic squamous non-small cell lung cancer. For further details regarding nivolumab, including its physical properties, pharmaceutical properties, pre-clinical studies, and toxicology, please refer to the Investigator's Brochure.

## 7.2.2. Ipilimumab

Ipilimumab (Yervoy®) is a recombinant, human monoclonal antibody that binds to the cytotoxic T-lymphocyte-associated antigen 4 (CTLA-4). Ipilimumab is currently FDA approved unresectable, metastatic, or cutaneous melanoma; advanced renal cell carcinoma in combination with nivolumab; microsatellite instability-high or mismatch repair deficient metastatic colorectal cancer that has progressed. For further details regarding ipilimumab, including its physical properties, pharmaceutical properties, pre-clinical studies, and toxicology, please refer to the Investigator's Brochure.

[figure not shown]
## 7.3. Study Purpose/Rationale

Treatment of a limited number of brain metastases includes a mélange of focused radiotherapy, neurosurgical resection, and carefully selected systemic therapy. The advent of immunotherapies merits new investigations into the order and timing of standard of care and novel approaches. In an article published in the New England Journal of Medicine, Tawbi et al report that systemic treatment of asymptomatic melanoma brain metastases with ipilimumab and nivolumab showed clinically significant intracranial responses with complete response rate of 26% [12]. Patients with symptomatic brain metastases have inferior intracranial response rates and are in need of novel strategies [13]. A similar study published in The Lancet Oncology showed clinical response of both melanoma and NSCLC metastatic to the brain to pembrolizumab (PD-1 inhibitor) treatment [14]. These response rates are respectable but leave room for improvement. Single agent PD-1 inhibition with nivolumab was ineffective in brain metastases from renal cell carcinoma with intracranial response rates of only 12% [15]. While the above trials have focused on adjuvant immunotherapy, the intent of the proposed study is to determine whether neoadjuvant immunotherapy would improve upon the current standard of care in patients with newly diagnosed brain metastases. Giving immunotherapies after surgery reduces T-cell receptor modulation, activating fewer tumor-specific T cells leading to a less robust immune response (Figure 1).

**Figure 1: Proposed mechanism for neoadjuvant immunotherapy t-cell modulation in GBM.** Taken from Cloughesy et. al.

Providing immunotherapies in the neoadjuvant setting, where antigenic burden is higher, should result in enhanced T-cell receptor modulation within the brain, and therefore more robust activation of tumor-specific T cells and an overall more effective immune response. Cloughesy et al reported in *Nature Medicine* that neoadjuvant treatment of surgically-resectable glioblastoma (GBM) with pembrolizumab resulted in significantly extended overall survival compared to patients who received adjuvant pembrolizumab (Figure 2) [16].

**Figure 2: Neoadjuvant treatment of surgically-resectable GBM with pembrolizumab results in significantly extended survival compared to adjuvant treatment.** Adapted from Cloughsey et al.

Importantly, **no patients in the neoadjuvant group experienced surgical delay**, suggesting that administration of checkpoint inhibitors prior to surgical resection is safe.

Given that immunotherapy, specifically nivolumab and ipilimumab, have been shown to have significant anti-tumor activity in brain oligometastases [12], and that administration of checkpoint inhibitors prior to surgery results in improved overall survival in patients with GBM [16], investigating the timing of immunotherapy administration in patients with brain metastases is clinically important. Towards this end, we have designed a single-arm clinical trial of neoadjuvant nivolumab and ipilimumab in patients with asymptomatic or minimally symptomatic brain metastases known to have spread from primary tumors that are traditionally responsive to immunotherapies. The percentage of patients experiencing surgical delay in the neoadjuvant treatment arm will be recorded to assess feasibility. Immunotherapy activity will be established by assessing the change in T-cell proliferation levels in circulation between baseline and Day 1 (see Section 12.7.5).

## 8. OBJECTIVES AND ENDPOINTS

	Objective	Endpoint	Analysis
Primary	Assess the feasibility of neoadjuvant ipilimumab and nivolumab treatment before surgery and SRS among patients with solid tumor brain metastases	Among eligible patients, the percentage of patients who experience surgical delay. Surgery is considered delayed if it occurs more than 10 days after ipilimumab and nivolumab, or never occurs, for reasons relating to the immunotherapy treatment.	See Section 15.5.1
Other Primary	Demonstrate that neoadjuvant immunotherapy will increase proliferation of circulating T-cells compared to baseline measurements	Mean fold-change between baseline and day 1 in Ki67 levels	See Section 15.5.2
Exploratory	Describe the survival of patients with solid tumor brain metastases receiving neoadjuvant ipilimumab and nivolumab followed by surgery and SRS.	Median survival	See Section 15.6.1
Exploratory	Describe the time to local intracranial progression	Median time to local intracranial progression	See Section 15.6.2
Exploratory	Describe the time to distant intracranial progression	Median time to distant intracranial progression	See Section 15.6.2
Exploratory	Describe the time to overall intracranial progression (local or distant)	Median time to overall intracranial progression (local or distant)	See Section 15.6.2
Exploratory	Describe progression-free survival	Median progression-free survival	See Section 15.6.2
Exploratory	Quantify the rate of radiation necrosis	Percent of patients with radiation necrosis	See Section 15.6.3
Exploratory	Describe immune express profiles	Normalized immune expression	See Section 15.6.4

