## 12. SCREENING AND ON-STUDY TESTS AND PROCEDURES

**Table 1: Schedule of Study Tests and Procedures**

Description	Screening	Treatment Period				
	Up to 14 days prior to surgical resection	Neoadjuvant IO	Surgery		Adjuvant SRS 	Follow-up
Week 		-1	1	3 	4	7, 13 +SOC visits
Day 		-10 to -4	1	15	22 ( $\pm$ 3 weeks)	29 + SOC visits
General Evaluations						
Informed Consent	X					
Physical Exam 	X	X	X	X		X
Neurologic Exam 	X	X	X	X		X
Performance Status 	X	X	X	X		X
Adverse Events					Continuous 	
Laboratory Evaluations						
CBC w/diff	X	X 	X	X		X
CMP	X	X 	X	X		X
Thyroid panel	X					X
PT, aPTT	X					
Pregnancy test 	X	X 				
Whole blood for correlative analysis (3x10 mL yellow top) 	X		X 	X	X 	X 
Archival tissue sample 	X					
Surgical tissue sample			X 			
Disease Evaluations						
MRI of the brain 	X					X 
Treatment						
Ipilimumab		X				
Nivolumab		X				
Surgery 			X			
SRS					X	

Number of fractions for SRS treatment will be assigned at physician's discretion

Weeks and days listed are approximate.

Post-operative visit

Clinical evaluations will include a general physical examination, complete neurologic examination, and KPS rating.

Adverse events will be continuously monitored after the first study-mandated agent is administered to the patient and reviewed monthly by the study PI. AE collection will cease 100-days after surgery, or 100 days after ipilimumab/nivolumab infusion for patients who do not undergo surgery.

Only drawn if more than 7-days (24-hours for pregnancy) post screening draw

For women of childbearing potential

Whole blood should be sent to the Substrate Services Core (SSCRS) for processing and then sent to [name] laboratory

Blood should be drawn prior to surgical resection

Blood should be drawn prior to SRS

Drawn only at the week 7 follow-up visit

A sample of archival tissue from the primary or other extracranial tumor will be requested for correlative analysis, if available.

A sample of tissue from the resected metastases will be requested for correlative analysis, if available.

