### **15.5.1. Primary Objective #1: Feasibility (Surgical Delay)**

#### **15.5.1.1. Variable**

The first primary objective is to demonstrate that neoadjuvant administration of ipilimumab and nivolumab administered to patients with solid tumor brain metastases before surgery and SRS is feasible. Feasibility will be assessed by the proportion of patients who have their surgery delayed or surgery never occurs as a direct or indirect result of ipilimumab and/or nivolumab treatment. With the checkpoint inhibitors being administered on Day -7, the surgery is scheduled for Week 1, Day 1 ( $\pm$  3 days). *Surgery will be considered delayed if it never occurs or occurs after Day 4 (i.e. Day 1 + 3).*

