#### **15.5.1.2. Continuous Monitoring of Feasibility and Analysis**

The proportion of patients experiencing surgical delay as defined in Section 15.5.1.1 will be computed as the number of patients with delayed surgery or whom never have surgery as a direct or indirect result of ipilimumab and/or nivolumab treatment divided by the total number of patients.

Neoadjuvant treatment patients who have delayed surgery or no surgery due to reasons unrelated to ipilimumab and/or nivolumab treatment will be excluded from the assessment of feasibility. However, this patient will be included in all other analyses if data is available. Reasons for such exclusions will be tabulated. All other patients will be considered evaluable for the assessment of feasibility.

Methods developed for continuous monitoring of toxicity will assess whether the number of surgical delays is not excessive. Based upon the Pocock boundary, the following monitoring rules were developed assuming that a true surgical delay rate of 10% is acceptable, and a surgical delay rate of 20% is too high. Accrual of patients will be suspended if the following conditions are satisfied:

# of Patients Enrolled to Date	Suspend Treatment Assignment if
1 – 4	# Evaluable Patients with Delayed Surgery > 1
5 – 8	# Evaluable Patients with Delayed Surgery > 2
6 – 14	# Evaluable Patients with Delayed Surgery > 3
15+	# Evaluable Patients with Delayed Surgery > 4

These monitoring rules were generated using the R software package. Specifically, the toxbdry function in the clinfun package (<https://cran.r-project.org/web/packages/clinfun/clinfun.pdf>) that implements methods developed by Jennison and Turnbull [20] and Ivanova et al [21] was used.

If accrual is suspended, the reasons for delay will be carefully reviewed to determine whether accrual should continue without any protocol modification, be permanently terminated, or whether modifications to the treatment regimen (e.g., removal of ipilimumab from the treatment regimen) should occur.

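### Do the two wordings of surgical delay, more than 10 days after infusion and after Day 4, define two different endpoints?

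*Combined protocol and SAP*

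**What the plan says.** The Endpoint column of Section 8 measures from treatment: "Surgery is considered delayed if it occurs more than 10 days after ipilimumab and nivolumab, or never occurs, for reasons relating to the immunotherapy treatment".

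Section 15.5.1.1 describes the schedule, "With the checkpoint inhibitors being administered on Day -7, the surgery is scheduled for Week 1, Day 1", with a window of ± 3 days on surgery, and then gives the rule: "Surgery will be considered delayed if it never occurs or occurs after Day 4 (i.e. Day 1 + 3". Section 5.6 repeats both statements. Sections 5.6 and 15.5.1.2 take the definition from 15.5.1.1; the latter speaks of "surgical delay as defined in Section 15.5.1.1 will be computed".

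The synopsis (5.3), the schema (6) and the design section (9.1) give only the interval: infusion 7 ± 3 days before resection. Table 1 and Section 12.2 label the infusion visit Day -10 to -4 and put surgery on Day 1. A footnote to Table 1 adds "Weeks and days listed are approximate".

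Two further provisions bear on reach. Under 15.5.1.2, patients whose surgery is late or missing "due to reasons unrelated to ipilimumab and/or nivolumab treatment will be excluded from the assessment of feasibility". If the delay count passes its limit, accrual is suspended while the reasons are reviewed to "determine whether accrual should continue without any protocol modification, be permanently terminated" or go on with a modified regimen.

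**The concern.** Surgical delay is the first primary endpoint and the count that drives the accrual-suspension rule, so it needs one cut-off. Section 8 anchors on the infusion, while 15.5.1.1 anchors on a study-day number. The two agree only if Day -7 is the day the patient was actually infused. Table 1 and 12.2 allow six other infusion days, and 15.5.1.1 speaks of surgery being scheduled for Day 1, which can be read as a planned date fixed in advance.

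On that reading, a patient infused on Day -10 and operated on Day 4 waits 13 days and is on time under 15.5.1.1 but delayed under Section 8. A patient infused on Day -4 and operated on Day 5 waits 8 days and is delayed under 15.5.1.1 but not under Section 8. With at most 20 patients, one immunotherapy-related case that changes class moves the observed rate by 1/20 = 5 percentage points, in a design whose monitoring rule separates 10% from 20%.

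**Working it through.** **Inputs.** Section 8 cut-off: more than 10 days after infusion. Section 15.5.1.1 cut-off: after Day 4, with infusion on Day -7. Interval in 5.3, 6 and 9.1: 7 ± 3, that is 4 to 10 days. Infusion labels in Table 1 and 12.2: Day -10 to Day -4.

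**Step 1: is there a Day 0?** Let D be the infusion day (negative) and S the surgery day (positive). Without a Day 0, elapsed days = S − D − 1; with one, elapsed days = S − D. For surgery on Day 1:

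| Infusion day | No Day 0 | With Day 0 |
|---|---|---|
| -10 | 1 + 10 − 1 = 10 | 11 |
| -7 | 1 + 7 − 1 = 7 | 8 |
| -4 | 1 + 4 − 1 = 4 | 5 |

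Only the no-Day-0 count returns the plan's 10, 7 and 4 days, so that is the numbering in use.

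**Step 2: the frame stated in 5.6 and 15.5.1.1.** With D = -7 and S = 4, elapsed = 4 + 7 − 1 = 10 days. Surgery after Day 4 is therefore surgery more than 10 days after infusion. The two wordings match on every surgery day, with 0 discordant days.

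**Step 3: the frame that creates the conflict.** Fix Day 1 as the planned surgery date and let D run from -10 to -4. Section 8 then means S − D − 1 > 10, or S > D + 11, against S > 4 in 15.5.1.1. The two thresholds differ by |D + 7| days:

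| Infusion day | Day 4 is infusion + | Delayed under Section 8 only | Delayed under 15.5.1.1 only |
|---|---|---|---|
| -10 | 13 days | Days 2–4 | none |
| -9 | 12 days | Days 3–4 | none |
| -8 | 11 days | Day 4 | none |
| -7 | 10 days | none | none |
| -6 | 9 days | none | Day 5 |
| -5 | 8 days | none | Days 5–6 |
| -4 | 7 days | none | Days 5–7 |

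The total is 3 + 2 + 1 + 0 + 1 + 2 + 3 = 12 pairs. The six in the third column lie 11 to 13 days after infusion, and the six in the fourth lie 8 to 10 days after it.

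**Step 4: is that frame in the plan?** Table 1 and 12.2 put the window on the infusion and hold surgery at Day 1. Sections 5.6 and 15.5.1.1 put the window on surgery and hold the infusion at Day -7. Each is a way of writing the same 4 to 10 day interval. The 12 pairs need both windows at once, which no section applies. In all 12, the Day 4 rule would also contradict the interval itself, passing as on time surgeries 11 to 13 days out and calling delayed those 8 to 10 days out.

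If Day 1 were instead the actual day of surgery, with the infusion counted backward, no operation could fall after Day 4 and the rule could never be met by a late surgery. The rule works as intended only in the Day -7 frame that its own section states.

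**The case for a change.** The strongest case for a change is that the anchor is not written down. Placing the infusion on Day -7 is not the same as defining Day -7 as the actual infusion date, and the visit schedule allows other days. No section says whether Day 1 is the planned or the actual surgery date. Sections 5.6 and 15.5.1.2 both send the reader to 15.5.1.1, so a programmer could take Day 4 literally, counted from a planned surgery date. In a trial of 20 patients one case is visible, and a clarifying note would cost almost nothing.

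The missing statement is real: for a patient infused off Day -7, the plan does not say how Day 1 is assigned. The step from there to a conflicting endpoint does not hold. Section 8 refers to 15.5.1 in its Analysis column; its Endpoint column carries its own complete rule, counted from infusion. The infusion anchor is therefore already in the plan, and 15.5.1.1 restates it in study days. The 5-point shift shows what moving any one patient does in a sample of 20. It does not measure this ambiguity, because the documents give no basis for saying that any patient would fall in the 1 to 3 day gap.

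**Conclusion.** No change follows. In the frame given by Sections 5.6 and 15.5.1.1, the Day 4 rule and the 10-day rule of Section 8 are the same limit, with no discordant days. What remains is an unstated day anchor for patients infused off Day -7. An analyst holding infusion and surgery dates would close that gap with the 10-day rule, the only reading that agrees with Section 8, with 15.5.1.1 and with the 7 ± 3 day interval. Writing it down would record that choice without altering the expected result.

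Even on the adverse reading the reach is narrow. It needs an infusion off Day -7 and a surgery within a gap of 1 to 3 days. Only immunotherapy-related delays enter the numerator, and reclassification can go either way. An unrelated late case that became an exclusion would move, for example, 2/20 = 10.0% to 2/19 = 10.5%. Crossing the suspension limit leads to a review, not to automatic closure.

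This rests on two assumptions: that study days have no Day 0, which the plan's own intervals imply, and that actual infusion and surgery dates are recorded. No case report form is shown, but Section 15.4 already plans to report surgery as on schedule, late or not done.
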